4 STUDY SCHEDULE

Informed consent will be obtained prior to the initiation of any protocol related activities.

4.1 SCREENING FOR ELIGIBLE PARTICIPANTS:

Patients who have been newly diagnosed with SDB and prescribed PAP for their treatment will be evaluated for eligibility, and if all entry criteria are met, they may be invited to participate in the study. This may be accomplished by phone or in person.

4.2 INITIAL (ENROLLMENT) CONTACT

1. Provide patient with access to informed consent document.
2. When consent has been obtained, collect device information (device ECN, device settings, mask type), demographic, and baseline data into the electronic data capture (EDC) system.
3. Randomize participant in EDC.
 - a. Participants randomized to the Control group (Group A) will complete a set of baseline questionnaires.
 - b. Participants randomized to the Treatment group (Group B) will complete a set of baseline questionnaires and provided with instructions to download Restful to their smartphone.
 - c. Monitor both groups' PAP device usage per your standard of care.

[figure not shown]
4.3 90-DAY STUDY CONTACT

1. Both Group A and Group B will be asked to complete a set of end of study questionnaires. Restful will be 'turned off' for Group B participants.
2. Continue to monitor participants' PAP device usage per your standard of care.
3. Distribute compensation for study participation.

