**Evaluation of an Incentive-based Intervention to
Improve 90-day Adherence in PAP-Naïve Patients:
Project Dahlia**

Investigational Plan

Version: **2.0**

Date: **08Jul2019**

Protocol Number: **SLP-18-08-01**

Sponsor: **ResMed Corp**
[name]
[name]
[contact]

NCT Number: **NCT03851094**

This protocol has been written in accordance with current applicable guidelines (IDE for USA) as well as all other relevant additional references, medical and legal.

The information herein is confidential and the property of ResMed Corp. It is to be used in confidence for the conduct of the clinical trial according to written agreement.

Version History

Version	Date	Notes
1.0	10Jan2019	Original Version
2.0	08Jul2019	Removed inclusion criteria for patients to have used their device less than an average of 3.5 hours of usage in the first 3 days of therapy.

Protocol Summary

Study Design:	
This is a prospective, randomized, open-label study to evaluate effectiveness of applying financial and social incentives via a smartphone-based app in helping participants achieve adherence to therapy. Randomization will consist of an allocation ratio of 2:1 (control:treatment)
 
This study will be conducted on patients with obstructive sleep apnea (OSA) who have been prescribed ResMed flow generator for positive airway pressure (PAP).
 
Participants will be randomized to one of two groups: control or intervention with Wellth app, "Restful". The study comprises up to 2 participant contacts by phone, and 3 data collection timepoints. The first contact involves consenting and enrolling the participant, providing instructions based on the arm they are randomized to, and collecting baseline data including questionnaires. Those randomized to the intervention group will have a second contact, which involves onboarding to Restful. A second administration of the questionnaires will occur at +90 days from baseline.

Intervention:	
Restful by Wellth. The intervention is use of the Restful app, which provides a small daily financial reward for achieving therapy usage goals and social support. The app will also send a daily reminder to participants to use their therapy. There is no clinical treatment intervention, as all patients included in this trial will be receiving PAP therapy per standard of care.

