3.2 STUDY DESIGN

This is a prospective, randomized, two-arm, open-label study to evaluate effectiveness of applying financial and social incentives via a smartphone-based app in helping participants achieve adherence to therapy. Randomization will include an allocation ratio of 2:1 (control:treatment).

Two 'site to participant' contacts are required during this study. These contacts can either occur at the clinical site or remotely (e.g., by telephone). During the initial contact, their interest in the study and eligibility will be confirmed, then they will be consented, asked to complete the Baseline Questionnaire, and their demographic information will be collected on case report forms (CRFs).

Participants randomized to the intervention (Group B) will be provided with information and assistance in downloading Restful to their smartphone and registering with Wellth.

At the final contact (90 days), the participant will be asked to complete an End of Study Questionnaire and the investigative staff will collect PAP therapy data for the trial period and record it on CRFs. Participants in Group B will have access to the Restful app discontinued. This completes the participant's active participation in the study.

Daily usage data from AirView will be collected and transmitted electronically from usage initiation to 90 days, and then through 180 days.

Study data will be captured on CRFs. See **Appendix A** for the **Baseline and End of Study Questionnaires**. See **Appendix B** for **Participant Instructions** related to the study procedures and the Restful app.

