3.8 ANALYSIS POPULATIONS

Randomized Population: all participants enrolled and randomized to treatment groups.

Intent-to-Treat (ITT) Population: all participants randomized to control or intervention group, regardless of the actual intervention received.

Evaluable Population: all ITT subjects who complete the 90-day study period and complete the end-of-study questionnaire.

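### The site procedure places the baseline questionnaires under randomisation, and no readable text requires them to be completed before the participant knows the arm

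*Combined protocol and SAP*

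**What the plan says.** Three places describe the first contact.

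- **Section 4.2** is the numbered site procedure. After consent, step 2 collects device information, "demographic, and baseline data into the electronic data capture (EDC) system". Step 3 is randomisation in EDC. The questionnaires are named only beneath it. Sub-step 3a reads "Participants randomized to the Control group (Group A) will complete a set of baseline questionnaires". In 3b, Group B participants "will complete a set of baseline questionnaires and provided with instructions to download Restful to their smartphone".
- **Section 3.2** says that, once consented, participants are "asked to complete the Baseline Questionnaire, and their demographic information will be collected on case report forms (CRFs"). The next paragraph turns to app set-up for Group B. Randomisation has no stated place in this sequence.
- **The Protocol Summary** (Study Design) describes the first contact as consenting and enrolling, "providing instructions based on the arm they are randomized to, and collecting baseline data including questionnaires". It puts Restful onboarding at a second contact.

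Section 3.2 also states "This is a prospective, randomized, two-arm, open-label study". At the 90-day contact (4.3), "Both Group A and Group B will be asked to complete a set of end of study questionnaires". Change in ESS and FOSQ-10 is a secondary endpoint in 3.7. Section 3.9 analyses it in two ways: a mixed-effects model with group, visit and their interaction on the ITT population, and a two-sample t-test on the Evaluable population. Section 3.8 defines that population as "all ITT subjects who complete the 90-day study period and complete the end-of-study questionnaire".

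**The concern.** A change score is a fair randomised comparison only if the baseline cannot depend on the assigned arm. ESS and FOSQ-10 are self-rated. A participant who already knows whether a paid incentive programme is coming may answer differently, or may not trouble to answer at all if assigned to control. Section 4.2 is the text that a site would work from, and taken literally it puts the questionnaires after allocation. Section 4.6 allows remote consent, with the same EDC login used for questionnaires later in the study, so nothing readable rules out a gap between allocation and completion.

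At stake is one of the three listed secondary endpoints. A baseline difference produced by knowledge of the arm would enter the estimated difference in change and could not be told apart from an effect of the intervention.

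**Working it through.** **Order of steps, side by side**

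| Source | Sequence as written | Leans to |
|---|---|---|
| 4.2, steps 3a/3b | consent; device, demographics, baseline data; randomise; questionnaires by arm | after |
| 4.2, step 2, using the Summary's usage of baseline data | baseline data (including questionnaires) before step 3 | before |
| 3.2 | consent; questionnaire; demographics; then Group B set-up | before, by list order only |
| Summary, word order | arm-based instructions; then baseline data including questionnaires | after |

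Section 4.2 puts demographics before randomisation, and 3.2 puts the questionnaire before demographics. If both lists are read as sequences, they disagree. But 3.2 may simply be a list of contents, so this is an inference from list order. No readable sentence says that the questionnaires must precede disclosure of the arm.

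**How a baseline shift would enter the result**

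Let b be the Test-minus-Control shift in mean baseline score caused by knowing the arm, and f the corresponding shift at 90 days. With a true difference in change of D, the expected estimate is D + f - b, so the bias is f - b. With every participant measured at both visits, the group-by-visit interaction estimates the same difference in change as the t-test, so the same expression applies to both. With questionnaires completed before allocation, b = 0 and the bias is f. The documents give no value for b or f, so no size or direction can be attached.

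**Missing baselines**

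The Evaluable definition does not ask for a baseline questionnaire. A participant without one has no change score and drops out of the t-test; the mixed model can still use the 90-day score. The t-test is therefore exposed if baselines are missing to different degrees in the two arms. The documents give no rate.

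**What is not affected**

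The sample size in 3.6 is for device-recorded usage, and its figures reproduce:

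- SE = sqrt(2.5²/180 + 2.0²/90) = sqrt(0.0347 + 0.0444) = 0.281, and 0.8/0.281 = 2.84.
- At one-sided 0.025, power is 0.811 by the normal approximation and 0.808 by the noncentral t.
- 270/0.9 = 300.

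The order of the questionnaires enters none of this. Medicare adherence is also device data. For the moderator tests, a baseline shift that is the same for everyone in an arm leaves the slope in that arm, and so the interaction, unchanged.

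**Separate precision gain**

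With equal SD σ at both visits and correlation ρ, the per-participant variance is 2σ²(1 - ρ) for change and σ²(1 - ρ²) for ANCOVA. The ratio is (1 + ρ)/2. For an assumed ρ of 0.5 it is 0.75 (25% lower), and for 0.7 it is 0.85 (15% lower). The documents give no ρ.

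**The case against.** The strongest reply is that there is no flat contradiction. Only 4.2 places the questionnaires relative to randomisation. Section 3.2 is a running summary, and 4.2 itself names baseline data and baseline questionnaires as separate items. This stands: a reader might infer two explicit opposing instructions, and the text does not contain them.

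Second, the material most likely to show the intended order (the figure in 4.2, the study flow in 4.5 and the Appendix A PDF) cannot be read here. This also stands, and it limits the finding to the readable text. The three written descriptions would still need aligning.

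Third, randomising in EDC is not the same as telling the participant. Sub-step 3b mentions the questionnaires before the download instructions, and the Summary puts onboarding at a later contact. So exposure to the app before baseline is unlikely on that account. What remains possible is knowledge of the arm, which no readable text prevents.

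Fourth, reordering removes b but not f. If the shifts at the two visits happened to be equal, the present order would cancel them and the new one would not. That is correct algebra, but nothing in the documents supports relying on it.

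A reader might also infer that the t-test would include people with no change score. It would not; they drop out.

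**Conclusion.** The point holds as an ambiguity in the procedure with a plausible route to bias. Followed literally, and with the arm disclosed, section 4.2 allows self-rated ESS and FOSQ-10 baselines to be taken after allocation in an open-label trial. That would affect both the t-test on change and the group-by-visit model. The conclusion rests on two conditions: that sites follow 3a/3b in written order, and that participants learn their arm before answering.

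A reader might go further and infer that baselines were in fact contaminated, or that the false-positive rate rises by a particular amount. The documents support neither. They give no SD, correlation or shift for these scales, and any error rate would only restate the assumed inputs. Size and direction are unknown, and the reach is limited to the ESS and FOSQ-10 change endpoint.

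**What to change.** Align the Summary, 3.2 and 4.2 to one order: consent; baseline questionnaires completed in EDC; randomisation; arm-specific instructions. State in step 2 of 4.2 that baseline data include the questionnaires, remove them from 3a and 3b, and have EDC require them before it releases the allocation. If the unreadable figure or flow chart already shows this order, only the wording needs to follow it. If questionnaires have already been collected after the arm was known, report that as a limitation.

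The cost is one reordered procedure and one EDC rule, with the same questionnaires. A few patients who never complete the baseline would not be randomised, and app start may be slightly delayed when questionnaires are completed remotely. Open-label reporting bias at 90 days remains and should be stated as a limitation of the ESS and FOSQ-10 results.

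Separately, and only once the baseline is pre-randomisation (the covariate must not itself depend on allocation), replace the two-sample t-test on change with ANCOVA of the 90-day ESS and FOSQ-10 scores on baseline. This needs no new data and one changed sentence in 3.9.

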3.9 DATA ANALYSIS

Baseline demographic and psychosocial factors will be summarized for each randomized group for ITT and Evaluable Populations. For continuous variables, such as age and PAP usage, the mean, standard deviation, median, and range will be presented. For categorical variables, such as gender, the number and proportion of participants in each category will be presented. Baseline demographics and psychosocial factors for the control and intervention groups will be compared with t-tests and Fisher's exact tests, as appropriate.

The primary analysis compares mean PAP usage at 90 days in the control and intervention groups using a two-way ANOVA on the ITT population. Randomization group and myAir usage (Yes/No) will be included as factors in the model. The interaction of the two factors will be considered, but will only be retained in the model if it is significant at the 5% level. Missing usage hours during a day will be imputed as 0 usage. A secondary analysis of mean PAP usage will be conducted using the Evaluable Population. A sensitivity analysis of the missing data assumption will be conducted by considering missing data as missing. In this analysis, participants with no usage data will be assumed to have a mean usage of 0 hours; other participants' mean usage will be calculated as the mean usage across nights for which there is data.

A subgroup analysis of the primary endpoint will be generated for patients who are identified as strugglers. A struggler is defined as a patient who uses their device for less than or equal to 3.5 hours/night during the first 3 days of usage. Mean PAP usage at 90 days will be compared in the control and intervention groups using a two-way ANOVA on the struggler population as described above. Descriptive statistics will also be presented for mean PAP usage, comparing strugglers and non-strugglers in control and intervention groups.

Adherence will be calculated for the ITT population from daily usage data using the Medicare definition for adherence (a patient is adherent if they use the device for more than 4 hours per night for 70% of the nights during the first 90 days of usage). Percent adherence will be compared between control and intervention groups using a logistic regression model on the ITT population. Randomization group, myAir usage, and the interaction of these two factors will be included in the model. Missing usage hours during a day will be imputed as 0 usage.

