Mean change in ESS and FOSQ questionnaire scales will be compared between control and intervention groups using a mixed-effects linear model on the ITT population and a two-sample t-test on the Evaluable population. In the mixed-effects model, the response variable will be the mean questionnaire score and the model will include randomized group, visit, and a randomized group by visit interaction as fixed effects and subject as a random effect.

Baseline perceived disease severity, claustrophobia, coping skills, and health literacy will be tested as moderators of the intervention's effectiveness. Baseline scores will be regressed on the primary outcome (usage), and then in a mixed-effects model, the response variable will be usage and the model will include baseline score, randomized group, and a randomized group by baseline score interaction as fixed effects and subject as a random effect.

An exploratory analysis will examine how engagement with the study is associated with PAP usage. Engagement will be measured as app usage (number of touches). A linear regression model with PAP usage as the dependent variable and engagement as the independent variable will be fit to all ITT subjects (engagement is zero for all control subjects). An exploratory analysis will also test whether the intervention has a direct or indirect effect on the following psychosocial factors: the pros and cons of change, self-efficacy, and social support. Finally, an exploratory analysis will test whether nomination of, and the extent of engagement with, a social support person moderates the intervention effectiveness.

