5.4 CONTROL GROUP

The control group will be monitored and managed per the site's standard of care with the exception of completion of questionnaires at baseline and again at 90 days after enrollment.

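### If two sites enrol, no model in section 3.9 contains site, so any site difference in usage costs the primary comparison a modest amount of precision

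*Combined protocol and SAP*

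**What the plan says.** The Protocol Summary gives the number of clinical sites as one or two. Section 4.2 has the site monitor both groups' "PAP device usage per your standard of care", and section 4.3 continues that arrangement after the 90-day contact. Section 5.4 adds: "The control group will be monitored and managed per the site's standard of care".

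On allocation, the text gives the 2:1 control-to-treatment ratio (Protocol Summary, 3.2 and 3.6) and one instruction in 4.2: "Randomize participant in EDC". It describes no strata, blocks or sequence method.

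The section 3.9 models are:

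- **Primary ANOVA**, repeated for the struggler subgroup: "Randomization group and myAir usage (Yes/No) will be included as factors in the model". The interaction is kept only if significant.
- **Adherence logistic model**: "Randomization group, myAir usage, and the interaction of these two factors will be included in the model".
- **ESS/FOSQ mixed model**: "the model will include randomized group, visit, and a randomized group by visit interaction as fixed effects and subject as a random effect".
- **Moderator model**: baseline score, group, their interaction and a random subject effect.
- **Exploratory engagement regression**: engagement only.

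None contains site, and no site-by-treatment summary is planned.

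**The concern.** The primary endpoint is mean PAP usage, and how a site monitors and manages its patients could plausibly affect it. The plan leaves that to local practice and allows a second site. Section 3.1 recruits from the site's own database, so case mix could differ as well. Site is known before randomisation and is already recorded, which makes it an obvious covariate. If it is left out, any difference between two sites stays in the error term. The sample size has little room for this: section 3.6 asks for 270 evaluable participants, and 267 is the smallest 2:1 total that reaches 80% power.

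**Working it through.** **Inputs from section 3.6.** Difference 0.8 h; SD 2.5 (control) and 2.0 (test); 180 and 90 participants; one-sided alpha 0.025; unequal-variance t-test.

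**Assumptions not in the documents.** Two sites with shares p and 1−p, and a difference D in mean usage that is the same in both arms. The main case is p = 0.5.

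**Step 1: reproduce the plan.** SE = √(6.25/180 + 4.00/90) = √0.07917 = 0.2814 h, with Welch df about 217. The noncentral t gives power 0.808. N = 267 gives 0.804 and N = 264 gives 0.799. Dropout: 270/0.9 = 300. The plan's figures hold, with no allowance for site.

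**Step 2: add a site difference.** Leaving site out adds p(1−p)D² to each arm's within-site variance. Section 3.6 does not say whether its SDs are within-site or total, so both readings are shown.

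- Within-site SDs, site omitted: SE = √((6.25 + p(1−p)D²)/180 + (4.00 + p(1−p)D²)/90). With site in the model, power stays at about 0.81.
- Total SDs, site added: the same formula with p(1−p)D² subtracted. With site omitted, power stays at 0.808.

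| D (h) | p(1−p)D² | SE, within-site SDs, site omitted | Power | N for 80% | SE, total SDs, site added | Power |
|---|---|---|---|---|---|---|
| 0.5 | 0.0625 | 0.2832 | 0.803 | 270 | 0.2795 | 0.813 |
| 1.0 | 0.2500 | 0.2887 | 0.788 | 279 | 0.2739 | 0.829 |
| 1.5 | 0.5625 | 0.2976 | 0.763 | 297 | 0.2642 | 0.854 |
| 2.0 | 1.0000 | 0.3096 | 0.730 | 321 | 0.2500 | 0.890 |

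A 70/30 split softens this slightly: with within-site SDs and site omitted, power is 0.804, 0.791, 0.770 and 0.742. These figures use the t-test of section 3.6 as the yardstick and ignore the myAir factor and the single degree of freedom spent on site.

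**Step 3: chance imbalance.** Under simple randomisation the difference between arms in site share has SD √(0.25 × (1/180 + 1/90)) = 0.0645. The estimate therefore shifts with SD 0.0645 × D, or 0.032, 0.065 and 0.097 h at D = 0.5, 1.0 and 1.5. This is the same quantity as in step 2: at D = 1.0, 0.07917 + 0.0645² = 0.0833, whose square root is the 0.2887 in the table.

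**Step 4: type I error.** In simulations of 10,000 trials each, with simple randomisation and site omitted, the one-sided error was 0.0242, 0.0241 and 0.0239 at D = 0.5, 1.0 and 2.0 h. With the list stratified by site and site still omitted, it was 0.0262, 0.0227 and 0.0166. The Monte Carlo error is √(0.025 × 0.975/10,000) = 0.0016, so the conservatism shows clearly only at 2.0 h. The direction is as expected: the true SE is then 0.2814, but the test uses 0.2887 at 1.0 h (ratio 1.03) or 0.3096 at 2.0 h (ratio 1.10).

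**The case against.** The strongest reply is that the problem may never arise. It needs a second site that enrols, and sections 3.1, 5.4, 6.3 and 7 all speak of the site in the singular. With one site there is nothing to adjust for. That stands, and it is why the fix is conditional.

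The size is also assumed. The documents give no site difference; an equal split is the worst case; and a gap of 1.5 h is nearly twice the 0.8 h effect the trial is powered for. Up to 1 h, the loss or the forgone gain is about 2 power points. The primary analysis is also on the ITT population with missing usage set to 0, so the number analysed may be nearer 200/100, where planned power is 0.847. All of this stands and limits the weight of the point.

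Three stronger readings are tempting, and the documents do not support them:

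- **A reader might infer that randomisation is unstratified.** The text is silent on the method, and the study-flow figure is not in the copy reviewed. One can say only that no stratification is specified.
- **A reader might infer that usage must differ by site by design.** Leaving care to local practice permits a difference but does not establish one.
- **A reader might count chance imbalance as a second harm, or as bias.** Under simple randomisation it is the same variance seen another way, and the unadjusted standard error already carries it. Within a site, both arms' usage is monitored under the same local practice, so the comparison remains valid.

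**Conclusion.** The point holds as a minor, conditional matter of efficiency. If two sites enrol and their mean usage differs, leaving site out of the models gives up some precision. For gaps of 0.5, 1.0 and 1.5 h between equal sites, the cost is about 0.5, 2 and 4.5 power points if the planning SDs are within-site (0.808 falling to 0.803, 0.788 and 0.763). If they are total SDs, the forgone gain is about 0.5, 2 and 4.6 points (0.808 against 0.813, 0.829 and 0.854). Type I error is not inflated. If the EDC list does stratify by site, omitting site makes the test conservative, so a site term helps whether or not the list is stratified. The documents do not support any claim that the primary result would be biased or the trial underpowered as planned.

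**What to change.** Add a sentence to section 3.9: if two sites enrol, site is a fixed factor in the primary and struggler ANOVAs, the adherence logistic model, the ESS/FOSQ mixed model and the moderator model. Because the study is open-label, this should be fixed before usage data are compared by arm. It would also help to state in section 4.2 whether the EDC list is stratified by site.

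The cost is one degree of freedom per model, with no extra participants or data. In the logistic model the odds ratio for adherence becomes conditional on site, and the report should say so. The gain in the ESS/FOSQ model is likely to be smaller, because its group-by-visit contrast is largely within participant. No change to the randomisation list during enrolment is needed, since the model term recovers most of the gain. With one site the sentence has no effect.
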